## 1.1 Primary objective

The primary objective of the study is to assess the efficacy of two doses of SOM3355 (200 mg taken twice daily [BID] i.e. 400 mg/day and 300 mg BID i.e. 600 mg/day over at least 8 weeks at maintenance dose) compared to placebo to reduce chorea in HD patients measured by the change from baseline in total maximal chorea (TMC) score (primary efficacy endpoint).

## 1.2 Secondary objective

The secondary objectives of the study are:

- To evaluate the safety and tolerability of two doses of SOM3355 (400 mg/day and 600 mg/day) compared with placebo in HD patients, with particular attention to depression and suicidality and to the cardiovascular hemodynamic parameters.
- To evaluate the efficacy of the two doses of SOM3355 (400 mg/day and 600 mg/day) compared with placebo on:
  - o the change of Clinical Global Impression (CGI-C),
  - o the change of Patient Global Impression (PGI-C),
  - o the percentage of responders based on the improvement ≥2 in TMC score,
  - o the percentage of change of TMC score.
- A pharmacokinetic (PK) sub-study in a subset of 24 patients will allow to determine the PK profile of the two doses of SOM3355 (200 mg BID and 300 mg BID) at steady state and to model PK-PD assessments of hemodynamic and cardiac parameters. Analysis of these data will be described in a separate document and the results will be also presented in a separate report.

Statistical Analysis Plan	Version 1.0		Page 7 of 37
Sponsor	SOM Biotech	Protocol No	SOMCT03

#### 1.3 Study design

[figure not shown]
This is an international, multicenter, double-blind, randomized, placebo-controlled, parallel-group Phase IIb study assessing two doses of SOM3355 (400 or 600 mg/day), taken as 200 mg BID or 300 mg BID, in patients presenting choreic symptoms related to HD.

Patients will be randomized at the inclusion visit (Visit 1) to one of 3 treatment arms to receive either SOM3355 400 mg/day, SOM3355 600 mg/day, or placebo, all given BID. Dosing will start with an up titration in the first 3 weeks and will be maintained at a fixed dose for 7 weeks. After 10 weeks, patients will down titrate to 1 capsule 200mg / day of study drug for 1 week, followed by 1 capsule / day of placebo to assess the effect of drug interruption.

The study will enroll 129 patients with a genetically proven diagnosis of Huntington's Disease (confirmed by HTT gene CAG repeats  $\geq$ 36), of mild to moderate severity (TFC score  $\geq$ 7) with choreic symptoms (TMC score  $\geq$ 10). The patients will be recruited in investigating sites in various European countries. Ambulatory patients will be recruited by reference centers for HD in collaboration with patient advocacy groups and the EHDN.

A sub-study will characterize the PK profile of the 2 doses (400 mg/day or 600 mg/day) given twice daily for at least one week in a subset of patients (n = 24) who consent to be hospitalized for 24 hours for blood sampling and cardiac and hemodynamic assessments.

Figure1

Total study duration 12 weeks (+1 or 2 weeks for screening) – 11 weeks under SOM3355 active drug

Statistical Analysis Plan	Version 1.0		Page 8 of 37
Sponsor	SOM Biotech	Protocol No	SOMCT03

The flowchart/schedule of events can be found in Table 1: Schedule of Activities by Visit of the protocol.

An independent data safety monitoring board (DSMB) will be established by the Sponsor. DSMB will assess at intervals the progress of the clinical trial and the safety for participants in reviewing accumulated data on safety, tolerability, and efficacy outcomes.

## 1.4 Planned sample size

Power calculation is based on results from previous trials that tested VMAT2 inhibitors (TBZ and deuterbenazine) on chorea in HD patients with TMC score as primary endpoint, which showed a standard deviation of 3.5 and 3.9 respectively, and a treatment effect compared to placebo in TMC score of -3.5 and -2.5 respectively.

The sample size will be a total of 129 patients. Eligible patients will be randomized in blinded fashion in a 1:1:1 ratio i.e. 43 patients in each arm (SOM3355 400 mg/day, SOM3355 600 mg/day, or placebo). Assuming a treatment difference of -2.5 points in the change from baseline of TMC score compared to placebo and a standard deviation of 3.5 (to ensure a clinically relevant effect of at least -2 in the study), 39 patients per arm will provide at least 80% power that at least 1 dose of SOM3355 will be significantly superior to placebo at the 2-sided 0.025 significance level. This is based on the use of a two-sided t-test for the mean TMC score change. For the primary endpoint, the overall type I error will be controlled using a Holm procedure. To account for a 10% dropout rate, 43 patients per arm (i.e., a total of 129 patients) will be enrolled.

## **2 GENERAL INFORMATION**

## 2.1 Background details

All study data will be transferred to a SAS database (version 9.4 or later) for statistical analysis purposes. Data will be imported from a Data Capture System OPVerdi and external data vendors (cf. Data Management Plan) via validated SAS programs.

The SAP will be finalized before database lock after agreement with the Sponsor on patient disposition and coding.

## 2.2 Deviations from the trial protocol with regard to statistical analyses

The following deviations from the protocol were identified as being important for the statistical analysis:

For the key secondary efficacy endpoint (Change from baseline in the Clinical Global Impression (CGI-C)) multiplicity adjustment will be applied.

Original text in protocol: The type I error will be set at 0.05 (two-sided) and the coverage level of confidence intervals to 95% for all secondary efficacy analyses. No multiplicity adjustment will be applied for the statistical inferences of the secondary efficacy endpoints.

Statistical Analysis Plan	Version 1.0		Page 9 of 37
Sponsor	SOM Biotech	Protocol No	SOMCT03

The revised definition in SAP only for key secondary endpoint: To preserve the family-wise error rate at the 0.05 level when comparing the two doses of SOM3355 versus placebo and comparing a primary endpoint and key secondary endpoint, statistical testing will be carried out using the Holm procedure for CGI-C if the primary endpoint is significant for both doses. The smallest p-value of the two comparisons will be first compared at the two-sided 0.025 level and if statistically significant, the other p-value will be compared at the two-sided 0.05 level.

## 2.3 Individual protocol deviations

Apart from violations of inclusion or exclusion criteria the table below lists conditions that may affect the evaluation of patient data and the proposed actions:

Condition	Decision Rule
Informed consent not given	Exclude from all data analyses.
Violation of any inclusion or exclu-	Potentially exclude from Per Protocol Population
sion criteria	(PP)
Patients not exposed to IMP	Exclude from Safety Analysis Population (SAF),
	Modified Intent-to-Treat Population (mITT) and
	Per Protocol Population (PP)
Premature discontinuation during the	Potentially exclude from Per Protocol Population
treatment period	(PP)
Less than 80% or more than 120%	Potentially exclude from Per Protocol Population
compliance with IMP intake	(PP)
No post-baseline assessment of the	Exclude from Modified Intent-to-Treat Population
TMC score	(mITT) and Per Protocol Population (PP)
Patients receiving prohibited treat-	Potentially exclude from Per Protocol Population
ments	(PP)
Patient received a treatment which	Exclude from Per Protocol Population (PP)
the patients was not randomized for	

A detailed review of all documented and derived deviations from protocol will be part of the Blinded Data Review Meeting (BDRM) before database lock. During this BDRM the impact of protocol deviations on the analysis will be assessed and the conclusions recorded. Also, additional deviations could be identified during the meeting.

A complete listing of documented and derived protocol deviations and the judgment for assessment of patient disposition will be signed before database lock. A description of protocol violations that led to exclusion from any analysis sets will be included in the CSR.

## **3 ANALYSIS POPULATIONS**

In general, the disposition of patients will be displayed for following populations, if applicable:

- All screened population (having signed ICF)
- Screening failures

Statistical Analysis Plan	Version 1.0		Page 10 of 37
Sponsor	SOM Biotech	Protocol No	SOMCT03

- Intention-to-Treat (ITT) population
- Safety (SAF) population
- Modified Intention-to-Treat (mITT) population
- Per-Protocol (PP) population

Population assignment of patients will be decided upon in a treatment-blinded DRM with the Sponsor before database lock. The proper flags for analysis sets exclusion (e.g., exclusion from PP set), will be included in the analysis datasets. The protocol deviation list should be finalized before database lock.

#### 3.1 Screen failures

Screen failures are patients who have consented to participate in the clinical trial by signing the Informed Consent. Form before performing the screening assessments but who did not meet all the selection criteria to be randomized at the inclusion visit V1, by consequence they are not eligible to be subsequently randomly assigned to the study intervention or entered in the study.

## 3.2 Intention-to-Treat (ITT) population

The ITT Population will include all randomized patients whether they received the study treatment or not. Patients will be analysed in the treatment group to which they were randomized, regardless of the treatment that was actually received or if they withdrew prior to first dosing.

## 3.3 Safety (SAF) population

The Safety Analysis Set (SAF) includes all patients who were administered at least one dose of any study drug. Patients who are randomized and assigned a treatment but withdrew prior to dosing will not be included in the safety population. Patients will be included in the treatment group based on the treatment actually received. The analysis of all safety variables will be based on the SAF.

## 3.4 Modified Intention-to-Treat (mITT) population

The mITT Population will include all patients from the ITT Population who were randomized to treatment, received at least one dose of study drug and had at least one post-baseline assessment of the TMC score. The primary efficacy analysis will be conducted on the mITT Population. Patients will be included in the treatment group to which they were randomized, regardless of the treatment that was received.

## 3.5 Per-protocol (PP) Population

The Per-Protocol Population (PP) is a subset of patients in the mITT.

Statistical Analysis Plan	Version 1.0		Page 11 of 37
Sponsor	SOM Biotech	Protocol No	SOMCT03

It includes all randomized patients who completed the study without important deviations from the protocol. The decision of the membership in the PP Population will be made during a blinded Data Review Meeting prior to database lock, reviewing all deviations occurred.

## 3.6 Subgroup analyses

Subgroup analyses of the primary efficacy (change in Total Maximal Chorea (TMC) score from baseline to the end of maintenance therapy at V5) are planned for the following subgroups:

- patients not taking neuroleptics during the study vs patients taking neuroleptics as concomitant medication during the study
- gender: male, female
- age: < median,  $\ge$  median
- country: France, Spain, UK, Poland, Italy, Germany
- baseline TMC: < median, ≥ median
- baseline TMS: < median, > median

This analysis will be performed on the mITT population, except the neuroleptics subgroup, which will also be repeated on the PP population.

Additional subgroup, correct versus incorrect down titration phase between Visit 5 and Visit 6, is defined as:

- patients who have performed a correct down titration phase i.e. who correctly took the IMP at half dose (1 capsule/ day) for a week and then capsules from placebo bottle for at least 4 days.
- patients who did incorrect down titration
  - o who took 2 capsules/day of IMP so remaining at full dose with no down titration, and then placebo with abrupt IMP discontinuation
  - o or who took the IMP at half dose (1 capsule/ day) for 2 weeks with no placebo wash out or less than 4 days under placebo

For this subgroup, only descriptive statistics on visits for the TMC score will be repeated on the mITT population to show the evolution of the TMC score between V5 and V6 after IMP interruption. In addition, time profiles of the mean TMC scores with standard error of the mean (SEM) will be presented.

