- Patients allocated to 400 mg/day treatment arm will receive 200 mg once daily (OD) the first week, and then 200 mg BID the second and third week.
- Patients allocated to 600 mg/day treatment arm will receive 200 mg OD the first week, 200 mg
   BID the second week, and then 300 mg BID the third week.
- Patients allocated to the placebo arm will take matching placebo capsules according to the same pattern, once a day during the first week and twice per day from the second week.

**Maintenance dose (from Visit 2 to Visit 5)**: the dose reached in each arm (200 mg BID or 300 mg BID or placebo) will be maintained for 7 additional weeks. At the end of this maintenance dose period, two evaluations will be performed one week apart, at Visit 4 (end of Week 9) and at Visit 5 (end of Week 10), to assess the treatment effect versus baseline.

End of study with 1-week down-titration and 1-week placebo washout (from Visit 5 to Visit 6): during the last 2 weeks (Week 11 and Week 12), the patients will be instructed to take only 1 capsule in the morning. The two arms receiving the active drug will be dispensed capsules dosed at 200 mg for one week to decrease the dosing to 200 mg/day. During the last week, all the patients will receive capsules of placebo.

Patients will return for a last visit (Visit 6) to assess the withdrawal of the drug.

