#### 4.3. RATIONALE FOR STUDY DESIGN

This 12-week Phase 2b study is designed to evaluate in parallel groups the efficacy, safety and tolerability of two doses of SOM3355 (400 mg/day or 600 mg/day, taken either as 200 mg or 300 mg BID) compared with placebo in HD patients with chorea. A previous Phase 2a study (SOMCT02) has already tested the effect of 400 mg/day SOM3355 (given as 200 mg BID) compared with placebo in a crossover design on 6-week periods, and it has shown a reduction of choreic symptoms measured by a significant decrease of the TMC score, and a good tolerability at the tested dose. For this Phase 2b trial, the regulatory authorities recommended a dose-finding study testing different fixed doses in parallel compared with placebo, to correctly assess the dose effect and determine the best dose to be tested in Phase 3.

It is deemed prudent to initiate the treatment by escalating the dose with weekly increases (200 mg OD the first week and 200 mg BID the second week to reach 300 mg BID on the third week for the patients allocated to the 600 mg/day treatment arm) for better tolerability and to reduce the risk of hypotension or bradycardia at the start of treatment. Then, the reached dose (400 mg/day or 600 mg/day) will be maintained for 7 additional weeks.

At the end of the maintenance dose, the study drug is down-titrated for one week (at 200 mg/day) to avoid an abrupt interruption of the dose, followed by a 1-week placebo washout period to assess the effect of the interruption of the study drug.

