# 8. CONDUCT OF THE STUDY

For each participant, the total treatment duration, from the inclusion visit, will be 12 weeks (+ 1 or 2 weeks for screening before inclusion) with a total of 7 visits.

The visit schedule and procedure assessments are listed in section 1.3.

This is an outpatient study, except for 24 patients that will be enrolled in the PK sub-study who will be hospitalized for 24 hours at Visit 2. HD patients come to visit their specialist at the hospital on successive time-points. All visits must be performed by investigators and sub-investigators qualified for this study and who are experts in the management of HD patients.

Visits are scheduled as follows:

•	V0 -	Screening visit:	at Day -7 to -14 max (Week -1 to -2 max)
•	V1 -	Inclusion visit (randomization):	at Day 0 (Week 0)
•	V2 -	End of up-titration:	at Day $21 \pm 2$ Days (Week 3)
•	V3 -	Interim visit at maintenance dose:	at Day $42 \pm 2$ Days (Week 6)
•	V4 -	End of maintenance dose #1	at Day $63 \pm 2$ Days (Week 9)
•	V5 -	End of maintenance dose #2	at Day $70 \pm 2$ Days (Week 10)
•	V6 -	End of study	at Day $84 \pm 2$ Days (Week 12)

If the date of one visit is changed (anticipated or delayed), the next visit should occur according to the original schedule.

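### SAP 3.6 pools patients off active drug at Visit 6 with patients still on it in one 'incorrect down titration' group, so that group does not show TMC after interruption; its dose labels fit only the 400 mg/day arm

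*SAP*

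**What the plan says.** Weeks 11 and 12 are a taper followed by placebo. Protocol 4.1 states: "The two arms receiving the active drug will be dispensed capsules dosed at 200 mg for one week", and all patients take placebo in the last week. Protocol 4.3 gives the purpose: the taper avoids an abrupt stop and is "followed by a 1-week placebo washout period to assess the effect of the interruption of the study drug".

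SAP 3.6 adds a descriptive subgroup display on the mITT population, intended "to show the evolution of the TMC score between V5 and V6 after IMP interruption". A patient is 'correct' after one capsule a day "for a week and then capsules from placebo bottle for at least 4 days". A patient is 'incorrect' by either of two routes:

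- Route A: patients "who took 2 capsules/day of IMP so remaining at full dose with no down titration, and then placebo with abrupt IMP discontinuation".
- Route B: one capsule a day "for 2 weeks with no placebo wash out or less than 4 days under placebo".

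On timing, protocol 8 sets Visit 5 at Day 70 ± 2 and Visit 6 at Day 84 ± 2, and adds: "If the date of one visit is changed (anticipated or delayed), the next visit should occur according to the original schedule".

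**The concern.** The two routes leave patients in opposite states at Visit 6. Route A patients skipped the taper but have stopped active drug. Route B patients have not stopped, or stopped at most a few days earlier. Averaging them gives a number that describes neither, in a display whose purpose is to show what happens after stopping. It also hides the patients who stopped without a taper. Since the taper exists to avoid an abrupt stop, taper versus no taper among patients who did stop is a comparison a reader would want.

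There are two smaller problems. The dose labels assume that one Week 11 capsule is half of every active patient's maintenance dose. And because both visits are tied to the original calendar, the protocol's own windows can shorten the placebo period below the 4 days that the SAP requires.

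**Working it through.** **Inputs.** Week 11 capsules are 200 mg in both active arms, and maintenance is 200 mg BID or 300 mg BID (protocol 4.1). A bottle holds 14 capsules (protocol 6.2). At Visit 5 the patient gets two bottles, takes one capsule a day for 7 days from each, takes the first dose at the visit, and takes none on the morning of Visit 6 (protocol 8.1.6). The windows are Days 68 to 72 and Days 82 to 86 (protocol 8).

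**1. The stated washout.** Placebo days = Visit 6 day − Visit 5 day − 7. At nominal days, 84 − 70 − 7 = 7. The protocol's one week reproduces.

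**2. Status at Visit 6, nominal visit days.**

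| SAP class | Pattern | Placebo days | Active drug at Visit 6 |
|---|---|---|---|
| Correct | 1/day for 7 days, then placebo | 7 | stopped |
| Incorrect, route A | 2/day, so 14 capsules last 14/2 = 7 days, then placebo | 7 | stopped |
| Incorrect, route B | 1/day for 14 days | 0 | still on |
| Incorrect, route B | short placebo period | 1 to 3 | only just stopped |

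Route A matches the correct group on time off drug and differs only in the taper. Route B is the one that differs on interruption.

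**3. Effect of the mix (illustration).** Assume that 2.5 TMC points return once the drug is stopped. This borrows the sample-size difference; the documents give no figure for loss of effect. Let f be the share of the incorrect group who are route B and still on drug.

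- If route B keeps the whole benefit at 200 mg/day, the pooled change is 2.5 × (1 − f): 1.9 at f = 25%, 1.25 at 50%, 0.6 at 75%.
- If route B keeps half, it is 2.5 × (1 − f) + 1.25 × f: 2.2 at 25%, 1.9 at 50%, 1.6 at 75%.

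In this example the correct group shows 2.5 throughout. The incorrect mean moves only because f or the retained benefit moves.

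**4. Dose labels.** Two Week 11 capsules are 2 × 200 = 400 mg/day: 400/400 = 100% of maintenance in the lower arm, 400/600 = 67% in the higher arm. One capsule is 200 mg/day: 200/400 = 50% and 200/600 = 33%. Both labels fit the 400 mg/day arm and neither fits the 600 mg/day arm. This assumes the capsules came from the Week 11 bottle. Leftover 300 mg capsules would change it, but patients are asked to return bottles at each visit.

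**5. Windows.** Five possible days for each visit give 25 pairs. Placebo days are distributed as follows: 3 (1 pair), 4 (2), 5 (3), 6 (4), 7 (5), 8 (4), 9 (3), 10 (2), 11 (1). The single pair below 4 is Visit 5 on Day 72 with Visit 6 on Day 82: 82 − 72 − 7 = 3. That patient can follow every instruction and still cannot be 'correct'. Read literally, route B asks for two weeks on active capsules, so this patient may fit neither class. These are counts of day pairs, not expected frequencies.

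**6. Can the errors be identified?** A route B patient who takes 14 capsules from the first bottle and none from the second has used 14 of 14 expected, or 100%, so the 80% to 120% rule does not flag it. SAP 4.4 also computes dose per bottle, however: 14 × 200 = 2800 mg from the first bottle against 7 × 200 = 1400 mg planned. That does reveal the error.

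**The case against.** A reader might infer that the drug-interruption question cannot be answered at all. The documents do not support that. The correct group is kept separate and requires at least 4 placebo days, so neither the pooling nor the 3-day case enters it. SAP 4 gives descriptive statistics by treatment group, so its change can be set beside placebo. SAP 4.7.1 also shows TMC by arm and visit, including Visit 6, although that summary mixes all dosing patterns.

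Nor do the windows routinely break the washout. Ten of the 25 pairs give fewer than 7 days, but the SAP's threshold is 4, and 24 of 25 meet it. The overall compliance percentage misses the no-washout error, but the per-bottle dose and the patient diary do not, so the trial will be able to see it.

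Keeping abrupt stoppers out of the correct group is also defensible, because the protocol planned an interruption after a taper. The dose labels do not change who is classified where, since the classes rest on capsules per day, and SAP 1.3 and 4.4 state the 200 mg Week 11 dose properly. Finally, Visit 6 is in no primary or secondary efficacy endpoint.

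All of this stands, and it limits the point to a minor one. It does not justify combining route A with route B, which is a different matter from keeping route A out of the correct group.

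**Conclusion.** The point holds in a limited form. The incorrect group joins patients who stopped active drug with patients who did not, so its mean, and the correct-versus-incorrect contrast, cannot be read as TMC after interruption. The correct group can. The full-dose and half-dose labels conflict with protocol 4.1 for the 600 mg/day arm, and one in-window visit combination leaves a compliant patient without a clear class.

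The pooling and the label conflict follow from the text alone. The size of the distortion does not: it rests on an assumed 2.5-point return, an assumed retained benefit, and a mix of errors for which the documents give no counts. Severity is minor. The display is descriptive, and the primary and secondary efficacy conclusions are unaffected.

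**What to change.** Amend SAP 3.6 before unblinding, so that the split cannot look data-driven. Report separately, by arm:

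1. taper, then at least 4 placebo days;
2. no taper, then placebo;
3. some placebo, but fewer than 4 days;
4. no placebo capsules before Visit 6.

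Rows 3 and 4 should stay apart, because a patient with 3 placebo days has stopped and a patient with none has not. A patient with no taper and 1 to 3 placebo days meets both rows 2 and 3, so the SAP should state which takes precedence.

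Classify from the per-bottle counts in SAP 4.4 and the diary. Apply the same capsule-pattern classification to the placebo arm, so that selected active patients are not compared with unselected placebo patients. Tabulate actual placebo days before Visit 6. Replace the full-dose and half-dose labels with actual mg/day per arm.

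Reconcile SAP 3.6 with the Week 11 dosing in protocol 4.1, and with the visit windows and stated one-week washout in protocol 8 and 4.3. How the windows and the washout are reconciled is for the sponsor; no new schedule is proposed here.

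The cost is SAP wording and a re-cut of one descriptive display (its table and the matching mean profiles), using data already planned. The downside is smaller cells.
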